6.12. Lifestyle Guidance

All subjects will receive counseling regarding lifestyle including the maintenance of a healthy diet and physical activity at the Screening visit. At each subsequent visit, subjects will be asked if there has been a significant change in diet or physical activity. Changes will be documented in the eCRF.

6.13. Clinical Laboratory Tests

6.13.1. Laboratory Parameters

Blood samples will be collected according to the Schedule of Assessments ([Appendix A - B](#)) and below. Samples will be sent to the central laboratory for analysis and reporting. Samples may be analyzed for the tests outlined in this protocol and for any additional tests necessary to ensure subject safety. These may include, but are not limited to, investigation of unexpected results and incurred sample reanalysis.

At visits where indicated, samples should be collected in the morning following an overnight fast of at least 8 or 12 hours.

Subjects will be in a seated, semi-recumbent, or supine position during blood collection. Clinical laboratory tests will include the following:

Table 5. Clinical Laboratory Assessments

Chemistry	Hematology/Coagulation	Urine/Miscellaneous	Biomarkers
Sodium	Hematology	Urine	Fibrosis Biomarkers
Potassium	RBC count	Drug screening: amphetamines, cocaine and opiates (i.e., heroin, morphine)	ELF
Chloride	Hemoglobin (Hgb)		Pro-C3
Bicarbonate	Hematocrit (Hct)		C3M
Calcium	Platelet count		NIS-4 ^d
Magnesium			
Phosphorus	WBC count with differential: neutrophils, lymphocytes, monocytes, eosinophils, and basophils	Miscellaneous	Bone Biomarkers
Glucose ^b		Screening Serology Tests	P1NP
BUN			CTX-1 ^b
Creatinine			
Total protein		HBsAg	Lipid Metabolism Biomarkers
Albumin	ANC	HBcAb	ApoB & ApoC3
Uric acid		HBV DNA	
LDH	Coagulation	Hep A IgM	
Total (TBL) and direct bilirubin	PT	Anti-HCV antibody	Insulin Sensitivity & Glycemic Control Biomarkers
Alkaline phosphatase (ALP)	aPTT	HCV RNA	Insulin
ALT (SGPT)	INR	HIV	Adiponectin
AST (SGOT)	PAI-1		C-Peptide
GGT	Fibrinogen	Endogenous FGF21 ^b	HOMA-IR ^b
CK			
hsCRP		Pregnancy test ^a	
Amylase			
Lipase ^c		Pharmacokinetics (PK)	
3 Hydroxybutyrate			
HbA1c			
Lipoproteins			
Lp (a)		Anti EFX antibody (ADA)	
NMR LipoProfile ^b (includes Total Cholesterol, HDL-C, LDL-C, LDL-P, Triglycerides)		Neutralizing Anti EFX antibody (NAB)	

ADA = anti-drug antibodies; ALT = alanine aminotransferase; ANC = absolute neutrophil count; Apo = Apolipoprotein; AST = aspartate aminotransferase; aPTT = activated partial thromboplastin time; BUN = blood urea nitrogen; ELF = Enhanced Liver Fibrosis panel; GGT = gamma-glutamyl transferase; HbA1c = Glycated Hemoglobin A1c; HBcAb = total hepatitis B core antibody; HBsAg = hepatitis B surface antigen; HBV DNA = hepatitis B virus deoxyribonucleic acid; HCV = hepatitis C virus; HDL-C = high density lipoprotein cholesterol; HIV = human immunodeficiency virus; HOMA-IR = Homeostatic Model Assessment of Insulin Resistance; hsCRP = high sensitivity C-Reactive Protein; INR = International Normalized Ratio; LDH = lactate dehydrogenase; LDL-C = low density lipoprotein cholesterol; LDL-P = low density lipoprotein particle; Lp = Lipoprotein; L&HMW = low and high molecular weight; NMR = nuclear magnetic resonance; PAI-1 = Plasminogen Activator Inhibitor-1; Pro-C3 = N-terminal Type III Collagen Propeptide; PT = prothrombin time;

RBC = red blood cell; RNA = ribonucleic acid; TBL, total bilirubin; WBC = white blood cell

^a For female subjects of childbearing potential only. Serum pregnancy test at screening and urine pregnancy test at other time points.

^b Samples to be collected in the morning following an overnight fast of at least 8 hours.

^c Reflex lipase testing is performed in subjects with total amylase > 1.5 ULN.

^d Samples to be collected in the morning following an overnight fast of at least 12 hours

6.14. Sample Collection, Storage, and Shipping

Blood and urine samples from screening through ET or Follow-up visits will be collected and submitted to the central laboratory for analysis. Validated assays will be used for analysis when appropriate.

6.15. Pharmacokinetic Assessments

Pharmacokinetic samples will be collected at time points specified in the Schedule of Assessments ([Appendix A - B](#)).

6.15.1 [REDACTED]

6.16. Anti-Drug Antibody and Neutralizing Antibody Sampling

Samples will be obtained for detection of anti-drug antibodies (ADA) against EFX as outlined in the Schedule of Assessments ([Appendix A - B](#)).

In the event of a positive anti-EFX antibody detection, a neutralizing ADA assay will be run for the sample timepoint with the positive result.

Subjects who test positive for binding antibodies to EFX at the final scheduled study visit will be required to return for additional follow-up testing. This testing is to occur once the site has been notified of the positive result and approximately every 3 months until: (1) antibodies are no longer detectable or (2) the subject has been followed for a period of at least 6 months (\pm 2 weeks) after administration of EFX. All follow-up results, both positive

and negative, will be communicated to the sites. More frequent testing (e.g., every month) or testing for a longer period of time may be requested in the event of safety-related concerns. Follow-up testing is not required where it is established that the subject did not receive EFX.

6.17. Blood Storage

A portion of the blood samples drawn at study visits will be frozen and stored. The stored samples may be used for future clinical laboratory testing to provide additional clinical data. No human genetic testing will be performed without expressed consent of study subjects. At the conclusion of the study, these samples may be retained in storage by Akero for a period of up to 15 years or per local guidelines.

6.18. Biomarkers

The biological specimens collected in this study will be used to evaluate the association of exploratory systemic biomarkers with study drug response, including efficacy and/or AEs and to increase knowledge and understanding of the biology of how EFX affects subjects with NASH. Biological specimens may also be used to increase the knowledge of diseases such as NAFLD, liver fibrosis, inflammatory diseases, bone turnover, and/or the validation of a companion diagnostic if applicable. The specific analyses will include, but will not be limited to, the biomarkers and assays described in [Table 5](#). As biomarker science is a rapidly evolving area of investigation, and AEs in particular are difficult to predict, it is not possible to specify prospectively all tests that will be performed on the specimens provided. The testing outlined is based upon the current state of scientific knowledge and may be modified during or after the end of the study to remove tests no longer indicated and/or to add new tests based upon the newest technologies.

Samples will be destroyed no later than 15 years after the end of the study. The specimen storage period will be in accordance with the IRB/IEC/EC approved ICF and applicable laws (e.g., health authority requirements).

6.19. Subject Retention

Given the burden of study assessments, long study duration, and potential commercial availability of treatments for subjects with NASH, maintaining subject retention in a long-term, placebo-controlled clinical outcomes study could be challenging. The objective of the subject retention plan is to describe the activities and tactics that can be implemented with the goal of retaining subjects on treatment and in follow-up through the clinical outcomes portion of the study. To achieve this objective, the following types of approaches may be applied:

Site Support and Tactics

Our aim will be to provide the sites with the support and tools to encourage behaviors that optimize subject engagement, retention and compliance:

- CRO staff and Akero staff will maintain regular contact (i.e. telephone calls or in-person as available) with the sites to specifically discuss retention and compliance at that site and to exchange and share experience and best practices.
- Site newsletters emphasizing retention tactics and metrics will be employed. Retention Training Webinars will be held to reinforce progress and share ideas across sites.
- Site support materials will be provided to motivate and assist sites in engaging in subject retention activities.
- CRO staff and Akero staff will continue to reinforce key behaviors with site staff such as: encouraging staff to continue building subject relationship, conducting regular check-in phone calls or video-capable telehealth engagements, office visit reminder phone calls and ensuring the Principal Investigator is present at study visits, talking directly to the subject and re-enforcing the importance of their study participation.
- Provide support to minimize lost to follow-up through use of a third-party investigative service to search for subject location and contact information, vital status research, and death certificate retrievals.

Details of the materials and tools to be utilized are outlined in the Subject Recruitment & Retention Plan.

6.20. Criteria for Discontinuation of Study Drug

Study drug must be discontinued in the following instances:

- Liver-related clinical event that warrants discontinuation as determined by the Hepatic Events Adjudication Committee.
- Subject develops an SAE consisting of a serious hypersensitivity reaction to study drug.
- Subject experiences diarrhea that meets the criteria in [Section 6.24](#) for discontinuation.
- Subject experiences a Grade IV Common Terminology Criteria for Adverse Events (CTCAE) or meets the criteria for Drug Induced Liver Injury described in [Section 6.26](#).
 - The Data Monitoring Committee (DMC) should perform a causality assessment. The study drug may be restarted if the DMC concludes that the AE or laboratory abnormalities were not related to study drug, the AE has resolved, laboratory abnormalities have returned to baseline, and the subject is amenable to close clinical follow-up.
 - If, after re-challenge, a subject has a second AE or recurrent elevations (even mild or minimal) of total bilirubin, ALT, or AST as defined in [Section 6.26.3](#), study drug should be discontinued permanently.

- Unacceptable toxicity or toxicity that, in the judgment of the Investigator or the Sponsor, compromises the ability to continue study-specific procedures or is considered to not be in the subject's best interest.
- Significant subject noncompliance including refusal to complete the Week 24 liver biopsy.
- Significant protocol violation that impacts subject safety.
- Pregnancy during the study; refer to [Appendix D](#).
- Discontinuation of the study at the request of Akero, a regulatory agency, or an IRB/IEC/EC.

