6.25.1. Hepatic Events Adjudication Committee

A key objective of this study is to prevent progression to cirrhosis and associated complications. Clinical events that constitute the clinical outcomes endpoint include:

- 1) Progression to cirrhosis as defined by a liver biopsy showing F4 fibrosis according to the NASH CRN classification, as assessed by the central reader.
- 2) Events of hepatic decompensation including:

- a) Clinically apparent ascites requiring treatment
- b) HE of Grade 2 or above (according to the West Haven criteria defined in [Appendix E](#)) requiring treatment
- c) Portal hypertension-related upper gastrointestinal bleeding identified by endoscopy and requiring hospitalization, including events of bleeding from esophageal varices, gastric varices, and portal hypertensive gastropathy
- 3) Liver transplantation or qualification for liver transplantation, defined as MELD score ≥ 15 (unless due to therapeutic anticoagulation) on at least 2 consecutive occasions at least 4 weeks apart
- 4) All-cause mortality

Each of the clinical events (except histologic progression to cirrhosis, all-cause mortality and liver transplantation) will require confirmation by a Hepatic Events Adjudication Committee. All deaths will be reviewed by this committee to determine if they are liver-related.

If there is clinical evidence that a subject has progressed to cirrhosis (e.g., based on the presence of new esophageal varices, changes in biomarkers [including, but not limited to, low serum albumin, high serum bilirubin, a low platelet count, prolonged INR, or elevated liver stiffness], or development of other clinical signs or symptoms of cirrhosis), the subject should undergo repeat liver biopsy for confirmation of progression to cirrhosis (F4 fibrosis as assessed by the central reader according to the NASH CRN classification) at the discretion of the principal investigator (PI).

Once the clinical event (except histological progression to cirrhosis, all-cause mortality and liver transplantation) is confirmed by the Hepatic Events Adjudication Committee, the subject will discontinue from the study. Subjects who experience histological progression to cirrhosis, all-cause mortality and liver transplantation will be discontinued from the study, but do not require confirmation from the adjudication committee prior to discontinuation.

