7.5. Estimands

In line with ICH E9 (R1) addendum, 5 attributes (treatment, population, endpoint, intercurrent events, and population-level summary) have been specified to translate the primary and key secondary efficacy objectives into treatment effects that are to be estimated (estimands).

The treatment conditions of interest are EFX 28 mg administered weekly, and EFX 50 mg administered weekly, and are compared with matching placebo administered weekly.

The treatment effect is assessed by the primary histological endpoint of improvement in liver fibrosis and no worsening of steatohepatitis.

The population of subjects targeted is adults with NASH with liver fibrosis as defined by the inclusion/exclusion criteria.

Intercurrent events are handled through a composite strategy (see Table 6).

The population-level summary of the treatment effect will be quantified by comparing observed responder proportions supported by the risk ratio of investigational product compared to placebo (EFX 28 mg versus placebo or EFX 50 mg versus placebo) calculated from the odds ratio obtained through Cochran-Mantel-Haenszel (CMH) test detailed in the Statistical Analysis Plan.

Table 6. Approach for Intercurrent Events for the Primary Endpoint

Intercurrent Event	Status
Start of additional therapy with potential to impact NASH condition (i.e. rescue medication)	Subject defined as a non-responder (even if a post-treatment biopsy is available)
MELD score ≥ 15	Subject defined as a non-responder (even if a post-treatment biopsy is available)
Hepatic decompensation event	
Unscheduled biopsy showing progression to F4	Subject will be counted as a non-responder
Bariatric surgery	Subject defined as a non-responder

The estimands attributes for all secondary histological endpoints are defined in the same manner as for the primary endpoint described above.

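### Sections 6.20 and 6.25.1 give the Hepatic Events Adjudication Committee different roles in discontinuation, and a subject who exits for F4 at Week 24 drops out of the Week 96 LBAS as a known progressor

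*Protocol*

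**What the plan says.** Protocol 6.20 opens with "Study drug must be discontinued in the following instances". The first entry is a "Liver-related clinical event that warrants discontinuation as determined by the Hepatic Events Adjudication Committee". Other entries stop drug without this committee: Grade IV events and drug-induced liver injury criteria (with a causality assessment by the DMC), and unacceptable toxicity (judged by the investigator or sponsor). F4 progression and transplantation are not named.

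Protocol 6.25.1 lists the outcome events. The first is "Progression to cirrhosis as defined by a liver biopsy showing F4 fibrosis according to the NASH CRN classification", as read centrally. The others are hepatic decompensation, transplantation or MELD-based qualification for it, and death. For the events that need adjudication, once the event "is confirmed by the Hepatic Events Adjudication Committee, the subject will discontinue from the study". Subjects with histological progression, death or transplantation "will be discontinued from the study, but do not require confirmation from the adjudication committee prior to discontinuation".

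On analysis, Protocol Table 6 (section 7.5) makes "Unscheduled biopsy showing progression to F4" a non-response for the primary endpoint. SAP 5.2 limits the LBAS to subjects with baseline and on-study biopsies at the matching time point, and notes that the Week 24 and Week 96 sets may differ. SAP 7.6.2.1 to 7.6.2.3 run the Week 96 histology endpoints on the LBAS first, then repeat them on the FAS, MFAS and Week 24 LBAS.

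**The concern.** A site working from 6.20 would look for a committee determination before stopping drug for a liver outcome. Section 6.25.1 asks for no determination of that kind: for F4 it asks the committee for nothing, and for decompensation or MELD qualification it asks only whether the event occurred. With no cross-reference, two sites could act differently on the same event.

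The statistical stake lies after Week 24. Every subject has a scheduled Week 24 biopsy, so F4 can be found there. Whether that subject remains in the study decides whether a Week 96 biopsy exists, and so whether the subject belongs to the lead set for the Week 96 histology endpoints. Losing subjects from that set because they progressed is selective, and the selection can differ between arms.

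**Working it through.** The core of this is a comparison of texts. The documents state no figure to reproduce.

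**Step 1: the two sections by event.**

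| Event | 6.20 (study drug) | 6.25.1 (study participation) |
|---|---|---|
| F4 on biopsy | Not named; at most covered by the general liver-event entry, which needs a committee determination | Exit, no committee confirmation |
| Transplantation | As for F4 | Exit, no committee confirmation |
| Decompensation, MELD qualification | Committee determines whether stopping is warranted | Committee confirms the event; exit follows |
| Liver injury criteria, Grade IV event, toxicity | Drug stops without this committee | Not covered |

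Rows 1 and 2 differ on whether the committee is involved. Row 3 differs on what it decides. Row 4 shows that the committee is not the only route in 6.20 to stopping drug. The removal list in 6.27 does not name F4 either.

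**Step 2: follow a subject whose scheduled Week 24 biopsy shows F4 and who exits under 6.25.1.**

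- Primary endpoint: entry requires F2 or F3, so F4 cannot be an improvement of one stage or more. The subject is a non-responder on the biopsy itself.
- Event-free survival (SAP 7.6.3.4, FAS): F4 on central reading is an event, and only the first event counts.
- Early-termination biopsy: apart from possible outcome adjudication, Appendix B footnote o asks for one only if the previous biopsy is at least 12 months old. A biopsy soon after Week 24 would also fall before Day 422, where the Week 96 histology window opens (SAP 6.1).
- Week 96 LBAS: no biopsy at the matching time point, so the subject is excluded.
- Week 96 FAS and MFAS: a missing biopsy is a non-response (SAP 6.2).
- Week 96 analysis on the Week 24 LBAS: missing is a non-response for two of the three endpoints (SAP 7.6.2.1 and 7.6.2.2). For fibrosis improvement alone, 7.6.2.3 limits that wording to the FAS.

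**Step 3: size in the Week 96 LBAS, by illustration.** The 40 per arm is from Protocol 5.2.2. Everything else is assumed: Week 96 responders 8 (placebo) and 20 (one EFX arm), every F4 subject a Week 96 non-responder, and every other subject biopsied.

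| F4 at Week 24 (placebo, EFX) | F4 subjects kept as non-responders | F4 subjects excluded | Shift |
|---|---|---|---|
| 4, 1 | 20/40 − 8/40 = 50.0% − 20.0% = 30.0 points | 20/39 − 8/36 = 51.3% − 22.2% = 29.1 points | 0.9 |
| 8, 2 | 30.0 points | 20/38 − 8/32 = 52.6% − 25.0% = 27.6 points | 2.4 |

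In both rows exclusion shrinks the difference, because more placebo subjects are assumed to progress. The size and direction depend on the F4 rate and its balance between arms.

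**The case against.** The strongest reply is that the sections do not conflict. Section 6.20 says when drug must stop and contains no word such as only. Section 6.25.1 says who leaves the study, and someone who has left no longer receives study drug. F4 is itself listed in 6.25.1 as a clinical event, so it can fall under the liver-event entry in 6.20, and 6.27 lets the investigator remove a subject at any time for safety. A site can satisfy both sections. This stands: inconsistent handling is a risk created by unlinked text, and the protocol nowhere prescribes it.

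A reader might go further and infer that under 6.20 an F4 subject stays on drug, with up to 95 − 24 = 71 further weekly doses, or that drug is never stopped for F4. The documents do not support this. Absence from a list of mandatory triggers is not permission to continue, and 6.25.1 requires exit.

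The reply also holds that the analysis is largely protected. The FAS, the MFAS and, for two of three endpoints, the Week 24 LBAS already count these subjects as non-responders. F4 found from Day 422 on falls in the Week 96 window, if an unscheduled or early-termination biopsy is within 21 days of the last dose. SAP Table 3 footnote 1 carries the primary endpoint's intercurrent-event rules to the secondary histology endpoints, and the content of SAP Table 1, which holds those rules, is not visible. It may cover a scheduled F4 biopsy, so the gap cannot be asserted from Protocol Table 6 alone.

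Finally, the LBAS shift is small, rests on assumed counts, and comes from the biopsy requirement. It would remain if both sections simply said that the subject leaves. That is also right, and it is why the fix has two separate parts.

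**Conclusion.** The concern holds in a limited form. The committee decides in 6.20 but only confirms in 6.25.1. For F4 and transplantation 6.25.1 bypasses it, 6.20 names neither event, and no text says how the sections fit together. The passages must be reconciled; this review takes no position on which clinical rule is right.

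The primary endpoint and first-event event-free survival are essentially unaffected. The remaining statistical weakness is that the lead Week 96 histology analysis excludes subjects who exit under 6.25.1 for F4 on the scheduled Week 24 biopsy, although their outcome is known to be unfavourable. The size is unknown because the documents give no F4 rate: 0.9 points with 4 and 1 assumed progressors, 2.4 points with 8 and 2. It would be wrong to infer a material bias in the trial's conclusions, since the supporting Week 96 analyses already count most of these cases as failures. The verdict assumes that SAP Table 1 does not already keep these subjects in the Week 96 LBAS analysis, which needs checking.

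**What to change.** First, align 6.20 and 6.25.1, with a cross-reference. For each 6.25.1 event (F4 on a scheduled or an unscheduled biopsy, decompensation, MELD qualification, transplantation) state whether study drug stops, whether the subject leaves the study, and whether the committee confirms the event, decides on discontinuation, or has no role. The sponsor chooses the rule.

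Second, check SAP Table 1. If it does not already do so, add a sentence keeping subjects removed under 6.25.1, including for F4 on the scheduled Week 24 biopsy, in the denominator of the Week 96 LBAS analysis as non-responders, and amend the definition in SAP 5.2 to allow it. This follows the composite strategy already chosen for the histological endpoints.

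The cost is wording in the protocol, the SAP and the committee charter, with no added visits or subjects. The downside is that the Week 96 LBAS would no longer consist strictly of subjects with a Week 96 biopsy; the strict version can be reported alongside.
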